6.3. Sample Size Determination

IRNF

The approach for sample size determination associated with the IRNF primary endpoint follows that of Zhou et al for the comparison of sensitivity and specificity of paired subject-level data arising from the test and predicate IRNF devices (Zhou 2002). Performance estimates used for the sample size calculations are based on internal engineering data.

Table 8: Sample Sizes for AF Cohorts of Subjects Required for IRNF Evaluation

Cohort	Required for 80% Power	Targeted for Enrollment to Observe AF Rhythm Presentation
Permanent AF (Cohort 4)	█	█
Non-Permanent AF (Cohort 3)	█	█
Total for AF Cohorts	█	█

Table 9: Sample Sizes for Subjects without AF Required for IRNF Evaluation

Cohort	Required for 80% Power	After Correction for Attrition
No Known Diagnosis of AF	█	█

Additionally, to assess the secondary endpoint hypothesis H_{02} of the study, an aggressor cohort of subjects with no known history of AF but with a known history of other arrhythmias which may resemble the irregularity of AF (i.e., frequent premature atrial contractions (PACs), frequent premature ventricular contractions (PVCs), supraventricular tachycardia (SVT), or non-sustained ventricular tachycardia (NSVT)) will be enrolled.

Table 10: Sample Sizes for Aggressor Subjects without AF Required for IRNF Evaluation

Cohort	Required for 80% Power	After Correction for Attrition and Rhythm Presentation
Aggressor Rhythms	█	█

AFBF

The approach for sample size determination follows the approach of Lu et al (Lu, 2016). The power associated with the primary endpoint hypothesis can be estimated as

$$Power = 1 - \Phi\left(\frac{\bar{D} + 1.96S_D - \delta}{se_{LOA}} - z_{\alpha/2}\right) - \Phi\left(\frac{-\bar{D} + 1.96S_D - \delta}{se_{LOA}} - z_{\alpha/2}\right)$$

where $\Phi(x)$ is the cumulative density function of the standard normal distribution, \bar{D} is the expected average difference in AF burden measurements between the device and reference method, δ is the maximum allowable difference, $z_{\alpha/2}$ is the cumulative $100(\alpha/2)\%$ percentile of the standard normal distribution, and se_{LOA} is the standard error of the lower or upper Limit of Agreement defined as $se_{LOA} = S_D * \sqrt{1/n + (1.96^2)/(2*(n-1))}$ where S_D is the standard deviation of the paired AFB differences.

[REDACTED]

To summarize, a total █ subjects will be enrolled into the study according to the cohorts below:

- n █ (Cohort 1: No Known Diagnosis of AF)
- n █ (Cohort 2: Aggressor Rhythm Cohort)
- n █ (Cohort 3: Non-Permanent AF)
- n █ (Cohort 4: Permanent AF)

6.4. Significance Level

The primary non-inferiority hypotheses test of sensitivity and specificity and the secondary endpoint non-inferiority comparison of false positive rates for the IRNF will use a one-sided

significance level of 0.025. If non-inferiority is demonstrated, a test of superiority will be performed using the same significance level.

All AFBF analyses will use a two-sided significance level of 0.05.

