2.2. Study Endpoints

Primary Endpoints:

IRNF:

- Sensitivity of the irregular rhythm notification for the identification of persons with AF by 13-day ambulatory ECG, with AF defined as at least 30 seconds of AF by ambulatory ECG.
- Specificity of the lack of irregular rhythm notification for the identification of persons without AF by 13-day ambulatory ECG, with AF defined as at least 30 seconds of AF by ambulatory ECG.

AFBF:

- Weekly AF burden estimate, defined as the percentage of time a subject is in Atrial Fibrillation during wrist device wear over the prior 7 consecutive days

Secondary Endpoints:

IRNF:

- Notification-level positive predictive value (PPV) with AF by ambulatory ECG at the time of any tachogram comprising the notification.
- Tachogram-level performance (Sensitivity, Specificity, false positive rate (FPR), PPV, negative predictive value (NPV)) for tachograms comprising alerts.
- Tachogram-level performance (Sensitivity, Specificity, FPR, PPV, NPV) for all generated tachograms.

AFBF:

- Sensitivity, specificity, positive predictive value, and negative predictive value of tachograms for the identification of AF by ambulatory ECG.
- Day-specific AF burden estimate defined as the percentage of time a subject is in Atrial Fibrillation during a specific day of the week.
- Four-hour segment-specific AF burden estimate defined as the percentage of time a subject is in Atrial Fibrillation during a specific four-hour segment of a day.

Study Hypotheses

IRNF:

The primary endpoint hypothesis associated with the IRNF is:

[REDACTED]

[REDACTED] Data from subjects in Cohorts 1, 3, and 4 will be used to test this hypothesis.

The secondary endpoint hypothesis associated with the IRNF compares the tachogram-level false positive rate (FPR) of the test device to that of the predicate device to determine if the test device algorithm FPR is non-inferior [REDACTED] to that of the predicate device using all tachograms generated only from subjects in Cohort 2 (Aggressor Rhythm Cohort). [REDACTED]

[REDACTED]

AFBF:

The primary endpoint hypothesis associated with the AFBF is:

[REDACTED]

The secondary endpoint hypotheses associated with the day-specific and four-hour segment-specific endpoints are listed below, respectively:

[REDACTED]

[REDACTED]
[REDACTED]
[REDACTED]
[REDACTED] Additional
information on the simulation methodology is contained in Section 6.2.3 and the SAP.

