6.2.2. Primary Endpoint Analysis

IRNF

Two separate tables will be generated for subject-level data cross-classified by the test device and the predicate device results as presented below for the data collected on all subjects in Cohorts 1 and 3, and 4. One table will be diagnosis of at least one AF episode of at least 30 seconds present on the ECG patch ([Table 5](#)) to assess sensitivity and the other table will be no AF episodes present on ECG patch ([Table 6](#)) to assess specificity per the ECG patch diagnosis definition presented in Section [5.5.2.1](#). AF will be defined as any AF of at least 30 seconds duration by ambulatory ECG patch report. A concordant notification is defined as ≥ 30 seconds of AF present on ECG patch as determined by AF onsets/offsets + cardiac technician overread during the time period defined by the first and last tachograms comprising the alert. A discordant

notification is defined as a notification that is not concordant. Each subject can be represented once and in only one of the cells of the tables below.

Table 5: Diagnosis of ≥ 1 AF Episode Present on ECG Patch

Test Device (IRN 2.0)		Predicate Device (IRN 1.0)		
		≥ 1 Notification		No Notifications
		≥ 1 Concordant	All Discordant	-----
≥ 1 Notification	≥ 1 Concordant	a	b	c
	All Discordant	d	e	f
No Notifications	-----	g	h	i

By defining N1 as the sum of all subjects in [Table 5](#) above, the sensitivity of the test device will be estimated as $(a+b+c)/N1$ and the sensitivity of the predicate device will be estimated as $(a+d+g)/N1$.

Table 6: No AF Episodes Present on ECG Patch

Test Device (IRN 2.0)		Predicate Device (IRN 1.0)		
		≥ 1 Notification		No Notifications
		≥ 1 Concordant	All Discordant	-----
≥ 1 Notification	≥ 1 Concordant	-----	-----	-----
	All Discordant	-----	r	s
No Notifications	-----	-----	t	u

By defining N2 as the sum of all subjects in [Table 6](#) above, the specificity of the test and predicate devices will be estimated as $(t+u)/N2$ and $(s+u)/N2$, respectively.

Usable wrist device data that aligns with and corresponds to the time interval during which the ECG patch is worn will be used for this analysis.

Only subjects in Cohorts 1, 3, and 4 will be included in the primary endpoint analysis.

[REDACTED]

[figure not shown]
[REDACTED]

[REDACTED]

[REDACTED]

AFBF

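### Section 6.4 gives each IRNF superiority test the full one-sided 0.025 and visibly sets no order, gate or adjustment between endpoints: the nominal chance of any false superiority claim is up to 7.3%

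*Combined protocol and SAP*

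**What the plan says.** Section 6.4 is not redacted. It covers two primary comparisons of the test with the predicate algorithm ("The primary non-inferiority hypotheses test of sensitivity and specificity") and one secondary comparison ("the secondary endpoint non-inferiority comparison of false positive rates for the IRNF will use a one-sided" level of 0.025). It then sets the rule for superiority: "If non-inferiority is demonstrated, a test of superiority will be performed using the same significance level".

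The populations are set elsewhere. For sensitivity and specificity, Section 6.2.2 says: "Only subjects in Cohorts 1, 3, and 4 will be included in the primary endpoint analysis". It also places each subject in one cell of one table only, so the subjects with AF on the patch and those without do not overlap. Section 2.2 restricts the FPR comparison to tachograms from Cohort 2, and Section 6.2.5 keeps subjects enrolled in Cohort 2 there at final cohort assignment.

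The wording of the IRNF hypotheses in Section 2.2 and the text after Table 6 in Section 6.2.2 are largely redacted.

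**The concern.** For a single endpoint, testing superiority after non-inferiority at the same level costs nothing, because a result that excludes zero has already excluded the margin. That argument does not carry over to several endpoints. Section 6.4 appears to allow a superiority claim on any of three measures, each at the full 0.025. It has no visible order among them, no split of alpha, and no rule linking one endpoint's superiority test to another's result.

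What is at stake is the error rate behind a claim that the new algorithm beats the predicate on some measure. A reader would take that rate to be 2.5%. For the set of three claims, it is not.

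**Working it through.** The plan states no familywise error rate, and the IRNF margins and performance rates are redacted, so there is no figure of the plan's own to reproduce.

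**Inputs**
- Level per test: a = 0.025, one-sided (Section 6.4).
- Tests: superiority of sensitivity, of specificity and of Cohort 2 FPR (Section 6.4, read as one test per endpoint).
- Subjects: disjoint across the three (Sections 2.2, 6.2.2, 6.2.5), so the tests are taken as independent.
- No interim analyses (Section 6.7), so no further inflation from that source.
- Assumption: p, the chance of showing non-inferiority on one endpoint when its true difference is zero, is 0.80 to 0.90. The documents give no value.

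**1. Separate tests, all three true differences zero**
- Sensitivity and specificity only: 1 − 0.975² = 0.0494.
- All three: 1 − 0.975³ = 0.0731.
- Bound under any dependence: 3 × 0.025 = 0.075.
- With equal positive correlations of 0.3, 0.5 and 0.9 between normal test statistics, the rate is 0.068, 0.063 and 0.042.

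A non-inferiority gate on each endpoint separately does not lower the 0.0731. Rejecting at zero already implies non-inferiority at the same level.

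**2. Non-inferiority gates that span endpoints**

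Section 6.4 does not say whether non-inferiority must be shown per endpoint or jointly. Three joint readings were tried, all with true differences of zero:

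| Reading | Formula | p = 0.80 | p = 0.90 |
|---|---|---|---|
| Sensitivity and specificity must both be non-inferior; FPR has its own gate | 1 − (1 − [p² − (p − a)²])(1 − a) | 0.063 | 0.068 |
| All superiority tests wait for both primary non-inferiority results | p² − (p − a)²(1 − a) | 0.054 | 0.064 |
| All three must be non-inferior first | p³ − (p − a)³ | 0.047 | 0.059 |

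Worked example, third row at p = 0.80: 0.512 − 0.775³ = 0.512 − 0.4655 = 0.0465. All three readings rise to 0.0731 as p approaches 1.

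**3. Primary superiority as one joint claim (both must win)**

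The joint claim has error of at most 0.025. Adding FPR gives a ceiling of 1 − 0.975² = 0.0494. That ceiling is approached when one primary measure is truly much better and the other is equal. If all three differences are zero, the rate is 1 − (1 − 0.025²)(0.975) = 0.0256.

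**4. Conservative tests**

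The figures above take each test to have exact size 0.025. The references list an adjusted Wald interval for paired proportions. Assume that method for specificity with 78 subjects (the Cohort 1 target in the synopsis) and total discordance of 2%, 5% or 10%; the documents show no rates. The true size of the specificity test is then about 0.01%, 0.24% or 1.1%. With the other two tests at 0.025, the total runs from 1 − 0.975² × 0.9999 = 0.049 to 1 − 0.975² × 0.989 = 0.060. With 200 subjects and 10% discordance, the specificity test has size 2.1% and the total is 0.069.

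**The case against.** The strongest reply is that a testing order may exist where it cannot be seen. The IRNF hypotheses are redacted. Section 6.3 refers to a numbered secondary hypothesis that no visible text defines, and several sections defer detail to the SAP. This stands to the extent that absence cannot be asserted. Against it, Section 6.4 is the section on significance levels, is intact, states a positive rule and points to no other text. The visible references to the SAP concern simulation, randomization and readable data.

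Second, Section 6.4 speaks of one test of superiority and Section 2.2 of one primary hypothesis, so three separate tests is a reading, though the natural one. And 7.3% needs tests of exact size. Both points stand, which is why the figure is given as a nominal maximum with a range.

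A reader might also draw stronger conclusions that the documents do not support:
- That superiority testing has no gate at all. The text has one: "If non-inferiority is demonstrated, a test of superiority will be performed". What is not visible is a gate between endpoints.
- That the plan provides for a secondary claim after the primary fails. No visible passage states such a rule; Section 6.4 is silent.
- That AFBF has the same defect, since Section 2.2 mentions "The secondary endpoint hypotheses associated with the day-specific and four-hour segment-specific endpoints" and Section 6.4 says "All AFBF analyses will use a two-sided significance level of 0.05". The AFBF hypotheses and decision rules are redacted, so neither the defect nor its size can be shown.

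**Conclusion.** The point holds for the IRNF superiority claims. As visibly written, Section 6.4 does not hold the chance of any false superiority claim at 2.5%. The nominal rate is up to 7.3%. That maximum rests on one superiority test per endpoint, independence from disjoint subjects, exact test size and three true differences of zero. Cross-endpoint non-inferiority gates, a joint primary claim or a conservative specificity test would each lower it. No reading examined keeps the maximum down to 2.5%.

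The effect is confined to superiority claims taken as a set. Each single test keeps its 2.5% level, and the primary non-inferiority conclusion is not affected. This is a change worth making, not a flaw that undermines the study's main result.

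**What to change.** If an order is already set in redacted text or the SAP, cross-reference it in Section 6.4. Otherwise add one paragraph there:

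1. Non-inferiority of sensitivity and specificity is tested first at one-sided 0.025, as now.
2. Non-inferiority of Cohort 2 FPR is tested formally only if step 1 succeeds.
3. Superiority of sensitivity, specificity and FPR is then tested by Holm at a total one-sided 0.025 (the smallest p-value against 0.025/3 = 0.0083, the next against 0.0125, the last against 0.025), or in an order stated in advance.

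The paragraph should say whether step 3 opens only after step 2 passes. If it does, the whole chain is held at 2.5%. If it does not, the superiority claims are held at 2.5% among themselves, but not together with the FPR non-inferiority claim. Holm has an advantage over a fixed order: a real gain in specificity is not blocked because sensitivity is merely equal.

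**Cost.** No extra subjects are needed and the power of the primary non-inferiority tests does not change. Superiority claims become somewhat harder to make, and the FPR result becomes descriptive if the primary fails. If each endpoint has 80% power independently (Tables 8 to 10 are headed with 80% power, but whether this applies per endpoint is an assumption), the chance of passing steps 1 and 2 is 0.8³ = 51%, against 80% for an ungated FPR test. The sponsor should accept that cost knowingly.

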6.5. Missing Data

Rigorous efforts will be made to ensure all subjects are compliant with the protocol. However, some subjects may drop out prematurely or some planned measurements may not be readable or interpretable. The data analyses will be conducted on all readable and interpretable data.

Additional details defining readable and interpretable data may be found in the study Statistical Analysis Plan (SAP).

6.6. Subgroup Analyses

In accordance with the FDA Guidance on the reporting of age-, race-, and ethnicity-specific data, the primary endpoints for both IRNF and AFBF devices will be reported by the following subgroups (data permitting). Some subgroups may be combined depending on data availability.

- Age group (<55; \geq 55 to <65; \geq 65 years)
- Sex (Male; Female)
- Race (White; Black or African American; Asian; American Indian or Alaska Native; Native Hawaiian or other Pacific Islander)
- Ethnicity (Hispanic or Latino; Not Hispanic or Latino)
- Wrist device series/configuration [REDACTED]
- Fitzpatrick Scale

6.7. Interim Analyses

There are no interim analyses planned in this study.

6.8. Analysis Sets

Full Analysis Set (FAS): All subjects who sign an informed consent and are enrolled into the study. This analysis set will be used to summarize subject and device accountability, demographic and baseline characteristics, and safety data. The data for this analysis set will be presented overall and separately for each of the final cohort designations.

ECG Patch Analysis Set (EAS): [REDACTED]

[REDACTED] This analysis set will be used to analyze the IRNF primary endpoint and additional subject-level sensitivity/specificity analyses.

ECG Patch Burden Analysis Set (EABS): All subjects in enrollment cohorts 3 and 4 with paired usable Watch and ECG patch data which provides for a weekly AF burden average measurement. This analysis set will be used to analyze the AFBF primary endpoint data.

Notification Analysis Set (NAS): All subjects with a IRNF 1.0 or IRNF 2.0 notification who have simultaneous, analyzable ECG patch data at the time of the notification. This analysis set will be used to analyze the secondary endpoint and additional notification-level endpoints.

Tachogram Analysis Set (TAS): All subjects with at least one tachogram paired with a readable ECG strip diagnosis. This analysis set will be used to analyze the secondary endpoint and additional tachogram-level endpoints for the IRNF and AFBF algorithms.

Sub-Study Analysis Set: All subjects who sign an informed consent and are enrolled into the sub-study which precedes the clinical validation study. This analysis set will be used to summarize subject accountability, demographic characteristics, and adverse event information.

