4. STUDY POPULATION

4.1. Subject Recruitment

Subject recruitment will abide by the guidelines of the IRB and the investigational site(s). Recruitment will continue until enrollment requirements are met, including reaching the targeted number of subjects completing the study procedures with adequate data collection. A subject will be considered enrolled if he/she has signed a consent form and participant has passed all screening criteria.

Investigators will keep a record, i.e. subjects screening log, of subjects who are entered into the study. Each subject must meet all the inclusion criteria and none of the exclusion criteria for this study at the time of screening and study participation. The Sponsor must approve any changes to the target distribution of subjects in writing prior to enrollment.

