5.1. Screening

Informed consent will be obtained before any study protocol-directed procedures are performed. After the signing of informed consent, the subject will be evaluated for eligibility according to the study inclusion/exclusion criteria (Section 4.3 and Section 4.4). This visit will be conducted remotely; in-person, on-site visits can occur only if approved by Sponsor.

During screening, the following should be obtained on each subject:

- Age
- Gender
- Race and ethnicity
- Diagnosed medical conditions
- Medications
- Allergies
- Occupation
- Visual assessment of general appearance and skin
- Body measurements and assessments (height, weight, BMI)*
- Skin tone assessment on Fitzpatrick scale
- Assessment of tattoos, moles, scars on wrist (both)

*Body measurements may be self-reported if the screening visit is conducted virtually.

5.2. Study Day 1

Subjects will report for the Day 1 visit at their scheduled date and time, which may be the same day as the screening visit if conducted in-person, on-site, but in no case more than 14 days after the screening visit. No special preparation for this visit is required. If eligibility is confirmed after completion of all screening procedures, subjects may begin study participation following the screening. This visit will be conducted remotely; in-person, on-site visits can occur only after Sponsor approval.

All subjects may take their normal medications on the day of the study and may eat normally prior to this visit.

Skin tone assessment on the Fitzpatrick scale will be confirmed at this visit.

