6.2.5. Additional Analyses

Subject accountability, device accountability, medical history, medication, demographic and baseline characteristics will be summarized by final cohort assignment for the reporting of results for the subjects included in the evaluation of the IRNF and AFBF devices. The final cohort assignments for subjects who self-report at the time of screening in Cohorts 1, 3, and 4 will be determined based on their final adjudicated reference ECG results of AF burden as follows:

- Cohort 1: Adjudicated AF Burden via reference ECG of 0%
- Cohort 3: Adjudicated AF Burden via reference ECG of >0% to <95%
- Cohort 4: Adjudicated AF Burden via reference ECG of $\geq 95\%$

The final cohort assignment of subjects who self-report at the time of screening in Cohort 2 will remain Cohort 2. If an adjudicated AF Burden measurement cannot be determined for a subject, the final cohort designation will be the same as the self-reported cohort at the time of screening. The rationale for reporting the results by final cohort designation is to most closely align the reporting of results based on the presentation or absence of AF during the study monitoring period regardless of prior diagnosis.

Additional efficacy analyses are described below.

IRNF

The performance at the person- and notification-level for AF and other arrhythmias (treated as a single combined category) by ambulatory ECG will be analyzed similarly to the corresponding primary and secondary endpoint analyses outlined above for the adjudicated diagnoses of only AF using all available data for subjects in Cohorts 1, 3, and 4. These additional analyses are distinct from the primary and secondary endpoint analyses in that the AF and other arrhythmia categories of diagnoses presented in Section 5.5.2.1 will be combined into a single category for purposes of analysis. In particular, the following performance parameters will be estimated and presented along with their associated 95% confidence intervals.

1. Sensitivity of the IRNF for the identification of persons for AF or other arrhythmias by up to 13-day (± 2 days) ambulatory ECG, defined as at least 10 seconds of AF or other arrhythmia by ambulatory ECG
2. Specificity of the lack of IRNF for the identification of persons without AF or other arrhythmias by up to (± 2 days) 13-day ambulatory ECG, defined as at least 10 seconds of AF or other arrhythmia by ambulatory ECG

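### By-cohort adverse event tables use a cohort label set after exposure, which early patch removal can change for some Cohort 3 recruits; the safety denominator also includes enrolled subjects who never reached Day 1

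*Combined protocol and SAP*

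**What the plan says.** Section 6.8 defines the FAS as "All subjects who sign an informed consent and are enrolled into the study" and uses it for accountability, baseline and safety summaries. It continues: "The data for this analysis set will be presented overall and separately for each of the final cohort designations". No visible analysis set limits the main study's safety summaries to subjects who were given a device or patch.

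Section 6.2.5 sets the final cohort of subjects screened into Cohorts 1, 3 or 4 from patch burden: 0% is Cohort 1, above 0% and below 95% is Cohort 3, and 95% or more is Cohort 4. Subjects screened into Cohort 2 stay there. There is also a fallback: "If an adjudicated AF Burden measurement cannot be determined for a subject, the final cohort designation will be the same as the self-reported cohort".

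Subjects who stop early are not kept out of this step. For those recruited to Cohorts 3 and 4, Section 4.2 determines burden after completion or termination. Section 7.2 allows data from a device removed early to be used if the quality is suitable.

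On the denominator, Section 4.1 says: "A subject will be considered enrolled if he/she has signed a consent form and participant has passed all screening criteria". Under the Schedule of Events, devices are handed out and the first patch is applied on Day 1. Section 5.2 allows Day 1 to fall on the screening day for on-site visits, "but in no case more than 14 days after the screening visit".

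**The concern.** The cohort label in the safety tables is an outcome of the monitoring period, and an AE can alter it. Section 1.4 names skin irritation from the patch and rash from the patch or wristband, and Section 4.5 lists an AE among the reasons for discontinuation. If a reaction ends patch wear, the recording is shorter. For a person with intermittent AF, a shorter recording is more likely to contain none. The reaction then helps to decide the column in which it is counted, and two cohorts with the same true rate can look different.

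The reason Section 6.2.5 gives for final cohorts is to align results with the AF actually seen during monitoring. That suits rhythm performance but has no bearing on skin reactions.

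The second issue is simpler. A subject who passes screening and drops out before Day 1 had no exposure, yet is counted in the denominator of every AE percentage.

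**Working it through.** **Enrolment figures (Synopsis).** The lower targets sum to 78 + 67 + 54 + 36 = 235 and the upper to 78 + 85 + 394 + 70 = 627, as stated. Adding the sub-study of about 40 gives 667, also as stated. The plan gives no AE rate, stopping rate or never-exposed share, so everything below is illustration on assumed inputs.

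**Reassignment: inputs**
- From the plan: 78 recruits in Cohort 1, 54 or 394 in Cohort 3, planned wear of 13 days.
- Assumed: a true reaction rate of 5% in both cohorts; reactions that end patch wear do so at day 3; 3 days suffice to adjudicate burden; intermittent AF episodes follow a Poisson process at 0.15 per day; Cohort 1 recruits show no AF.
- Varied: the share of reactions that end wear (all, or one in five), and the share of Cohort 3 persistently in AF (none, or half, with these kept in Cohort 3 for simplicity).

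**Chance of recording 0% burden in t days:** exp(−0.15 × t).
- 3 days: exp(−0.45) = 0.638
- 13 days: exp(−1.95) = 0.142

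**Largest case, step by step** (Cohort 3 n = 394, all intermittent, every reaction ends wear)
- Stop early: 394 × 0.05 = 19.7. Of these, 19.7 × 0.638 = 12.56 move to Cohort 1.
- Complete: 374.3. Of these, 374.3 × 0.142 = 53.25 move.
- Final Cohort 1: reactions 78 × 0.05 + 12.56 = 16.46; subjects 78 + 12.56 + 53.25 = 143.81; rate 11.4%.
- Final Cohort 3: reactions 19.7 − 12.56 = 7.14; subjects 394 − 65.81 = 328.19; rate 2.2%.

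**All cases** (percentages from unrounded counts; the true rate is 5% in both cohorts)

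| Reactions ending wear | Cohort 3 persistently in AF | Cohort 3 n | Final Cohort 1 | Final Cohort 3 | Both combined |
|---|---|---|---|---|---|
| All | None | 394 | 11.4% | 2.2% | 5.0% |
| All | None | 54 | 6.5% | 2.2% | 5.0% |
| One in five | None | 394 | 6.4% | 4.4% | 5.0% |
| One in five | None | 54 | 5.3% | 4.4% | 5.0% |
| One in five | Half | 394 | 5.9% | 4.7% | 5.0% |
| One in five | Half | 54 | 5.2% | 4.7% | 5.0% |

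The direction is the same throughout. The size depends mainly on how many reactions end patch wear and on how large Cohort 3 is. The combined rate does not move.

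**Movement upward.** Short wear can also push a subject into Cohort 4. A burden of at least 95% allows 0.05 × 312 h = 15.6 h out of AF over 13 days, but only 0.05 × 72 h = 3.6 h over 3 days. One long episode early in wear may then be enough.

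**Denominator.** If a share u of enrolled subjects is never exposed, the FAS rate is the exposed rate × (1 − u). A 10% rate becomes 10% × 0.95 = 9.5% at u = 5%, and 10% × 0.90 = 9.0% at u = 10%.

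**The case against.** The strongest reply is that the main safety result is safe from reassignment. Section 6.8 presents the data overall as well as by cohort, and moving subjects between columns cannot change the total. The study is classed as non-significant risk, all cohorts follow the same wear procedures, and no visible text plans a between-cohort safety test. All of this stands, and it limits the point to the descriptive breakdown.

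A reader might infer that any early stopper tends to be moved into Cohort 1. The documents do not support that. Cohort 2 never moves. Permanent AF will rarely show 0%, and most Cohort 1 recruits are already there. Cohort 3 also takes persistent and chronic AF, requires AF in the past 12 months, and excludes subjects on rhythm control medication with a history of zero burden. The fallback further protects anyone whose recording is too short to adjudicate. The visible text gives no minimum, and Section 6.5 leaves the definition of readable data to the SAP. If 3 days is not enough, the illustrated shift disappears for those subjects.

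A reader might also take 11.4% against 2.2% as the expected size. It is near the unfavourable end: it needs every reaction to end patch wear at day 3, a wholly intermittent Cohort 3, and recruitment to the ceiling of 394. Section 7.1.1 lists wrist events as possible AEs, and these need not stop the patch. Section 7.1 includes mild events that disrupt nothing.

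On the denominator, the never-exposed share is unknown and may be small, particularly where Day 1 coincides with screening. Device accountability is reported on the same set, so non-exposure should be largely visible. The AE percentages as planned would still include those subjects.

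**Conclusion.** The point holds in limited form. The plan tabulates AEs by a label that is fixed after exposure and that an AE can influence. The distortion concerns Cohort 3 recruits with intermittent AF who stop the patch early with an adjudicable recording. They lean towards final Cohort 1, with some possible movement into Cohort 4. For an equal 5% reaction rate, the planned table could show from about 5.2% against 4.7% up to 11.4% against 2.2% for final Cohorts 1 and 3. Those figures rest on the assumed episode rate, stopping share and day, mix of AF types, and the premise that 3 days of recording is adjudicable.

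It would go too far to conclude that the overall safety finding is biased by reassignment; it is not. The overall percentages are affected only by the unexposed denominator, in proportion to the never-exposed share. No endpoint or hypothesis changes. This is a cheap improvement to descriptive safety tables.

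**What to change.** In Sections 6.8 and 6.2.4, define a safety set of subjects who had a wrist device or ECG patch applied. Summarise AEs on it overall and by enrollment cohort, and list any events before Day 1 separately. Keep the FAS and final cohorts for accountability and baseline tables, and final cohorts for performance reporting. Grouping by enrollment cohort is already familiar to the plan: Section 6.8 defines the patch burden analysis set by enrollment Cohorts 3 and 4.

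The cost is a few sentences, one exposure flag and one more analysis set. No new data are needed. AE percentages may rise slightly once unexposed subjects leave the denominator.
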